Hospitalized patients with comorbid COPD who are at high risk for readmission will be recruited. Specifically patients with comorbid COPD who are to be discharged with (a) admission diagnosis of COPD (GOLD stage II or greater); AND (b) either a prior non-elective hospitalization (one in the past 12 months) OR active smoker. Such participants will undergo questionnaire-based screening for sleep-disordered breathing (STOP-BANG questionnaire) and if they have a high risk for SDB (≥ 3 points) will undergo an overnight portable sleep study for screening prior to hospital discharge (AHI ≥ 10 per hour; $>3\%$ oxygen desaturation for hypopneas). Sites may exercise the option of using the STOP-BANG questionnaire as a screening tool for the purposes of enriching the study population.

Participants who exhibit AHI ≥ 10 per hour; $>3\%$ oxygen desaturation for hypopneas based on the portable sleep test will undergo a PAP “wash in” daytime exposure for 30 minutes after adequate mask-fitting, on the therapy device (AVAPS- AE). Participants who fail to tolerate such therapy, or indicate that they would be unable to use such therapy at night, will not be randomized. Considering the “wash-in” is performed prior to randomization, such participants will not be included as part of the intention to treat (ITT) analysis.

After randomization and prior to discharge, participants will either be initiated on AVAPS-AE therapy (intervention arm) for 60 days or will be referred to the sleep center for further diagnostic testing and therapy initiation (standard of care arm). Participants will complete quality of life questionnaires (Functional outcomes of sleep questionnaire [FOSQ]) at baseline (in-person), and in 30 and 60 days (by mail) post discharge. If participants assigned to the intervention arm are discharged with home O₂ therapy, the O₂ will be entrained into the AVAPS-AE device for nighttime use. At time of hospital discharge, if participants in the intervention arm are not meeting conventional daytime and nighttime criteria for O₂ therapy [(SpO₂ $<88\%$ in room air –day) (> 5 continuous minutes SpO₂ $\leq 88\%$ - nighttime)], they will undergo AVAPS-AE therapy alone.

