4. Number of hospitalizations over 3 years (optional if enrolled in registry)
5. Time to re-hospitalization alone
6. Composite end-point of time to occurrence of non-emergent healthcare utilization (such as scheduled hospitalization, scheduled physician office, urgent care visits or emergency room visits).

IV. Subject Selection

Inclusion criteria:

1. Hospitalized patients who are at high risk for readmission who are at least 18 years of age.
2. Specifically patients with (a) a primary or secondary admission diagnosis of COPD who are ready for discharge AND (b) are also found to have sleep-disordered breathing (AHI \geq 10 per hour; $>3\%$ oxygen desaturation for hypopneas) by overnight portable respiratory study prior to hospital discharge.
3. Bedside spirometry revealing evidence for obstructive lung disease (post-bronchodilator; GOLD stage II or greater (FEV1 $<70\%$ predicted post BD).
4. No previous home PAP or NIV use within the past year

Exclusion criteria:

1. Central sleep apnea (Central apnea index >5 per hour; and/or $>50\%$ are central apneas & hypopneas)
2. Clinically unstable, i.e., hypotensive shock, uncontrolled cardiac ischemia or arrhythmias, requiring life support ventilation or as otherwise determined by the investigator
3. Participants with Stage III & IV Chronic Heart Failure as defined by the New York Heart Association (NYHA) Classification
4. Known or expected contraindications for the use of non-invasive ventilation per the assessment of the investigator.

A Pilot, Multi-Center, Randomized, Open-Label, Parallel Group Study to Assess the Effects of a Novel Application of Averaged Volume Assured Pressure Support Ventilation (AVAPS-AE) therapy on Re-hospitalization in Patients with Sleep-Disordered Breathing with co-morbid COPD.

Confidential

5. Lack of medical insurance

V. Study Enrollment

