Participants who are screened for enrollment will be entered on a screening log which will be maintained at the clinical site. Participants referred for screening will be given a thorough explanation of the study and the requirements for participation by the study coordinator or other qualified medical professional. If the participant is interested in the study, the investigator or a member of his/her staff should approach the patient to obtain written informed consent. The background of the proposed study, the benefits and risks of the procedures and study should be thoroughly explained to the participant. The participant must sign the consent form prior to enrollment. This form or a modification of it must have prior approval of the study site's Institutional Review Board (IRB). Failure to provide informed consent renders the participant ineligible for the study.

Up to 10 sites will be recruiting for this study. Up to 80 participants will be enrolled across all sites with the goal of 60 participants (N=60) completing the study (25% attrition rate). One site should not enroll more than 25% of total N.

VI. Study Procedures

Screening Assessment

Hospitalized patients with comorbid COPD who are at high risk for readmission will be recruited. Specifically patients with comorbid COPD who are about to be discharged, with (a) prior hospitalization (within the past 12 months) Such participants will undergo questionnaire-based screening for sleep-disordered breathing (STOP-BANG questionnaire) and if they have a high risk for SDB (≥ 3 points) will undergo an overnight screening portable sleep study the night prior to hospital discharge (AHI ≥ 10 per hour; $>3\%$ oxygen desaturation for hypopneas). Sites may exercise the option of using the STOP-BANG questionnaire as a screening tool for the purposes of enriching the study population.

Spirometry

Each participant will undergo a spirometric assessment, using a handheld Koko™ unit, to determine if they meet inclusion criteria.

Spirometry will be performed based on the "Standardization of Spirometry – 2005".¹¹ Acceptability and reproducibility criteria are summarized in Table 8 of the ATS document. Spirometry equipment must be calibrated with a 3L syringe prior to the first use daily. The results will be printed and maintained in a calibration log, which will routinely be monitored for compliance during monitoring visits. Spirometry

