A Pilot, Multi-Center, Randomized, Open-Label, Parallel Group Study to Assess the Effects of a Novel Application of Averaged Volume Assured Pressure Support Ventilation (AVAPS-AE) therapy on Re-hospitalization in Patients with Sleep-Disordered Breathing with co-morbid COPD.

Confidential

values recorded on the CRF will be post bronchodilator. Participants will need to reveal evidence for obstructive lung disease Gold stage II or greater (FEV1 < 70%) in order to continue in the study.

Diagnostic Overnight Sleep Study

Site investigators will make appropriate documentation in the study participants chart that they will be undergoing an overnight sleep study. In addition, results of the sleep study will be communicated to the participant by the site investigator and documented appropriately.

Either an Alice Night One (Philips Respiration) will be used for the overnight diagnostic sleep study. The Alice devices are portable home sleep testing devices that records information about breathing. It is used to diagnose OSA. These devices may be used in a sleep lab or clinical setting by trained professionals, or it may be used at home by patients as directed by their health care provider. Participants who are found to have sleep disorder breathing (AHI \geq 10 per hour) will qualify. It is known that supplemental oxygen that is titrated to maintain oxygen levels above 90% does not allow for easy differentiation of hypopneas. Therefore, for participants who require supplemental oxygen at night, oxygen will be titrated not to exceed 90% saturation at the start of the study on the night of the sleep test during calm wakefulness while lying in hospital bed at patient-determined head-elevation.

During the diagnostic sleep study, participants will be set-up with on with the portable device that includes the following sensors:

- An effort belt will be secured around the chest to measure movements associated with breathing effort
- Nasal cannula
- A flexible finger sensor placed on the finger to measure oxygen saturation (average signaling time of 3 seconds) and pulse

Scoring

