Two different quality of life questionnaires will be used in this study. Quality of life questionnaires are important tools for measuring health status changes in participants receiving an intervention. The general health questionnaire that measures functional health, well-being, and physical and mental health (SF-36) will be used in this study. The disease specific quality of life questionnaire (Functional Outcome of Sleep Questionnaire, FOSQ) will also be used in this study. Participants will be asked to complete these questionnaires prior to discharge.

Randomization

Following the completion of the screening procedures to determine study eligibility, participants will be randomly assigned to one of two study arms: 1) Intervention Group (AVAPS-AE), or 2) Standard of Care (SOC). A randomization website will balance the therapy assignments within each of the three classifications of COPD severity: Gold Stage 2, 3, and 4. The research sites will attempt to balance recruitment between stage-3 and stage-4 patients; however, enrollment of stage-2 patients will be capped at 10, as this severity comprises a small proportion of the hospitalized patients with COPD.

Intervention Group:

AVAPS settings:

• Target Tidal Volume	8 ml/kg of ideal body weight
• Pressure Support Min / Max	4 / 26 cmH ₂ O
• Max Pressure	30 cmH ₂ O
• EPAP Min / EPAP Max	4 / 20 cmH ₂ O
• Rate	Auto

Participants in the intervention group will be sent home the AVAPS-AE therapy device. They will receive one on one training on the device as well as a user manual

SOC Group:

A Pilot, Multi-Center, Randomized, Open-Label, Parallel Group Study to Assess the Effects of a Novel Application of Averaged Volume Assured Pressure Support Ventilation (AVAPS-AE) therapy on Re-hospitalization in Patients with Sleep-Disordered Breathing with co-morbid COPD.

Confidential

Standard of care: Portable sleep test results will be communicated to the participant and their health care provider. Timing and determination of further evaluation and treatment of the participant's sleep disordered breathing will be per their participant's health care provider's usual care pathway. Sites with change in usual care pathways that involve immediate initiation of PAP therapy as a standard practice will remain in the study. Such data will be analyzed in "per-protocol analysis". Participants in the SOC arm will receive phone calls to promote medication adherence.

Post Discharge Study period (60 days)

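### Inclusion criterion 3 asks for obstructive lung disease, but its only numeric test is FEV1 below 70%, which cannot show obstruction; no FEV1/FVC limit is given

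*Combined protocol and SAP*

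**What the plan says.** Section IV (Subject Selection), inclusion criterion 3, asks for "Bedside spirometry revealing evidence for obstructive lung disease (post-bronchodilator; GOLD stage II or greater (FEV1 $<70\%$ predicted post BD". Section VI (Study Procedures), Spirometry, says that the handheld test is done "to determine if they meet inclusion criteria", and adds: "Participants will need to reveal evidence for obstructive lung disease Gold stage II or greater (FEV1 < 70%) in order to continue in the study". The word predicted is absent there.

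Section II (Study Design) describes the target patient as having an "admission diagnosis of COPD (GOLD stage II or greater" and gives no FEV1 figure. The separate diagnostic requirement, inclusion criterion 2, is met by "a primary or secondary admission diagnosis of COPD who are ready for discharge".

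GOLD stage is then used in section VI, Randomization: "A randomization website will balance the therapy assignments within each of the three classifications of COPD severity: Gold Stage 2, 3, and 4". In addition, "enrollment of stage-2 patients will be capped at 10". Section VII (Statistical Analysis) lists baseline COPD severity among the adjustment covariates.

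No section available for review gives an FEV1/FVC limit or any other numeric test of obstruction. None gives the FEV1 bands for stages 2, 3 and 4, and the reference list contains no GOLD document.

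**The concern.** Criterion 3 has two parts: a requirement in words (obstructive disease, GOLD II or worse) and a number in parentheses that reads as its working meaning. The number does not test what the words ask for. FEV1 % predicted grades how reduced FEV1 is. It is low in airflow obstruction, but also when lung volume as a whole is reduced, and only its relation to FVC separates the two. Up to 10 sites would apply the criterion, and the number is the one part they can all apply in the same way.

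The other entry rules do not fill the gap. A secondary chart diagnosis is enough, spirometry is the step meant to confirm it, and no exclusion criterion addresses other causes of a low FEV1. Every participant must have sleep-disordered breathing, and the analysis plan lists body mass index as a covariate, so obesity-related restriction is a plausible mimic. The documents give no prevalence for it.

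At stake are the identity of the population and the meaning of the strata. Specific aim 1 is about patients hospitalised with co-morbid COPD. The same undefined staging governs stratification and a recruitment cap, and is the natural measure of the severity covariate.

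**Working it through.** The 70% threshold is a definition, so there is no calculated figure to reproduce. The check sets the sections side by side and then applies the written number to example patients.

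**Step 1. What each section supplies**

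| Place | Requirement in words | FEV1 limit | FEV1/FVC limit |
|---|---|---|---|
| II, Study Design | COPD admission diagnosis, GOLD II or above | none | none |
| IV, criterion 2 | primary or secondary COPD diagnosis | none | none |
| IV, criterion 3 | obstructive disease, GOLD II or above | post-bronchodilator, below 70% predicted | none |
| VI, Spirometry | obstructive disease, GOLD II or above | below 70%, reference not named | none |
| VI, Randomization | GOLD 2, 3, 4; stage 2 capped at 10 | none | none |

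**Step 2. The written number applied to examples**

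The values are illustrative. The FEV1/FVC cut-off of 0.70 is an assumption and is not in the documents.

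| Patient | FEV1 % predicted | FEV1/FVC | FEV1 below 70%? | FEV1 below 70% and FEV1/FVC below 0.70? |
|---|---|---|---|---|
| A, no obstruction | 60 | 0.80 | pass | fail |
| B, obstruction | 60 | 0.60 | pass | pass |
| C, severe obstruction | 40 | 0.50 | pass | pass |

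A and B have the same FEV1, so no rule based on FEV1 alone can separate them. With a secondary COPD diagnosis, patient A meets the number and can be given a GOLD stage.

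**Step 3. Scale**

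Section V (Study Enrollment) gives up to 80 enrolled and 60 completing. The share without obstruction is not given, so the shares below are assumed.

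| Assumed share | Of 80 enrolled | Of 60 completing |
|---|---|---|
| 5% | 80 × 0.05 = 4 | 60 × 0.05 = 3 |
| 10% | 80 × 0.10 = 8 | 60 × 0.10 = 6 |
| 20% | 80 × 0.20 = 16 | 60 × 0.20 = 12 |

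The stage-2 cap limits this. If all unobstructed patients were staged 2, there could be at most 10, which is 10/80 = 12.5% of enrolment. Reaching 16 would need at least 16 − 10 = 6 of them staged 3 or 4. Within the cap, each such patient uses 1/10 = 10% of the stage-2 places.

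**The case against.** The strongest reply is that the protocol does require obstruction. Criterion 3 and the Spirometry procedure both say so, and criterion 2 separately requires a COPD diagnosis, so patient A fails the words even though he or she meets the number. If the GOLD label carries an FEV1/FVC requirement with it, the label already supplies the missing test. Label and number can also be read together, as obstructed patients below a 70% FEV1 ceiling. This much stands: the requirement is present, and what it lacks is an operational test. It does not remove the point, because the protocol neither reproduces nor cites a GOLD definition and the only test it writes down is FEV1.

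It also stands that the consequence is limited. Eligibility is fixed before randomisation and applies to both arms, and no sample-size, power or alpha figure depends on it.

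Three stronger readings are tempting, and the documents do not support them:

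- A reader might infer that the GOLD II label and FEV1 below 70% select different patients, namely those at 70% to 79%. That holds only if the stage II ceiling is assumed to be 80%. The documents give no ceiling, and if it is 70% there is no such gap. Nor does the Study Design overview, which states no FEV1 limit, make anyone eligible who fails a listed criterion.
- A reader might infer that the 70% is an FEV1/FVC cut-off put in the wrong place. That is a guess about intent.
- A reader might infer that a treatment effect would shrink in proportion to the unobstructed share. That assumes the device does nothing for those patients. The background section says that it also treats coexisting obstructive sleep apnea, and every participant must have an AHI of at least 10 per hour.

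**Conclusion.** The concern holds as a defect in the eligibility and staging definitions. Obstruction is required in words, the only number offered cannot show it, and the stage boundaries used for stratification and the stage-2 cap are not stated. A patient with a chart diagnosis of COPD but no airflow obstruction can meet the number and be randomised within a GOLD stratum.

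The effect is on who is studied and what the strata mean; the comparison between arms stays unbiased. The number of patients affected cannot be derived from the documents, and the 4 to 16 of 80 rests entirely on an assumed 5% to 20%, with the upper end hard to reach under the stage-2 cap. The conclusion relies on one measurement fact, that FEV1 alone does not identify obstruction, and does not depend on where GOLD places its stage limits. It should be corrected, but it does not undermine the trial's validity.

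**What to change.** 1. In inclusion criterion 3 and the Spirometry procedure, state two post-bronchodilator conditions: an FEV1/FVC limit (for example below 0.70, for the sponsor to confirm) and an FEV1 % predicted ceiling. Record the ratio on the CRF.
2. Choose one FEV1 ceiling and use it, with the word predicted, in Study Design, criterion 3 and Spirometry. If 70% is kept, present it as an explicit limit of its own and not as the meaning of GOLD stage II.
3. State the FEV1 bands that the randomisation website uses for stages 2, 3 and 4. The same bands should govern the stage-2 cap and, if severity is analysed by stage, the severity covariate.

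The cost is amendment wording and at most one added CRF field. FVC comes from the same spirometry, so no extra test is needed. The drawback is some additional screen failures, which may slow recruitment.

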Participants who exhibit AHI ≥ 10 per hour; $>3\%$ oxygen desaturation for hypopneas based on the portable sleep test will undergo exposure for 30 minutes after adequate mask-fitting on the therapy device (AVAPS- AE; see device settings under section below entitled, "Standard Procedures and measurements prior to discharge"). Participants who fail to tolerate such therapy, or indicate that they would be unable to use such therapy at night, will not be randomized. Considering the "wash-in" is performed prior to randomization, such participants will not be included as part of the intention to treat (ITT) analysis.

Participants that are placed on PAP therapy during admission and tolerate the therapy will not be subjected to this aspect of the trial. Their experience, during the hospital visit, with the therapy will count as the PAP Wash-In.

Standard Procedures and measurements prior to discharge

Room Air SpO₂ assessment/Supplemental Oxygen

A room air SpO₂ measurement will be used to make a determination if supplemental oxygen is required prior to hospital discharge. SpO₂ should be collected with the participant breathing room air for at least 15 minutes prior. If participants cannot maintain a SpO₂ of at least 90% on room air, supplemental oxygen will be prescribed. If the participant requires supplemental oxygen (according to the guidelines stated

A Pilot, Multi-Center, Randomized, Open-Label, Parallel Group Study to Assess the Effects of a Novel Application of Averaged Volume Assured Pressure Support Ventilation (AVAPS-AE) therapy on Re-hospitalization in Patients with Sleep-Disordered Breathing with co-morbid COPD.

Confidential

below), but was not previously prescribed supplemental oxygen, the study investigator will prescribe it for the participant.

Data collection will consist of key demographic characteristics including gender, age, height, and weight. In addition, a medical history, physical exam, vital signs, medication assessment and Charlson co-morbidity index will all be collected/obtained.

Quality of Life Questionnaires

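### Sections II and VI state different criteria for supplemental oxygen, and Section II's apply to the intervention arm only, so oxygen can differ by arm after randomisation

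*Combined protocol and SAP*

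**What the plan says.** **Section VI, Room Air SpO₂ assessment/Supplemental Oxygen.** The room-air "measurement will be used to make a determination if supplemental oxygen is required prior to hospital discharge". If participants cannot hold an SpO₂ "of at least 90% on room air, supplemental oxygen will be prescribed". No arm is named and no night-time criterion is given. The closing sentence, on participants not already on oxygen, opens "If the participant requires supplemental oxygen (according to the guidelines stated" and points below, but no guidelines follow in the text available. The study investigator writes any new prescription.

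**Section II, Study Design.** Intervention participants discharged on home oxygen have it fed into the device at night. The next sentence, set at the time of discharge, says that "if participants in the intervention arm are not meeting conventional daytime and nighttime criteria for O₂ therapy", then "they will undergo AVAPS-AE therapy alone". The criteria in its brackets are room-air SpO₂ below 88% by day, and "> 5 continuous minutes" at or below 88% at night. There is no matching sentence for the standard-of-care (SOC) arm.

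**Related text.** Section II places randomisation before discharge, and the trial is open-label. Section VI describes the SOC arm's sleep-disordered-breathing care as usual care and gives no oxygen rule for that arm. Randomisation is balanced on GOLD stage only. The covariates listed under Statistical Analysis do not include oxygen.

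**The concern.** Both sections are current and both are worded as instructions. Two investigators who follow the protocol could therefore manage the same participant differently. Because one rule names a single arm, the difference can also line up with allocation.

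Oxygen is a respiratory treatment given alongside the device. The primary endpoint is time to a composite of emergent utilization: re-hospitalization and unscheduled office, urgent-care and emergency-room attendance. If discharge oxygen differs by arm because of the wording, the comparison is of the device plus a different oxygen policy. The right name for this is a post-randomisation co-intervention difference (performance bias), not confounding, because randomisation itself is intact.

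Little in the plan would reveal such a difference. Home oxygen at discharge is not an explicit item in the Section VI data list, although the medication assessment or the treatment records gathered for costing might pick it up.

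**Working it through.** The plan states no figure on this point, so the check is to apply both rules to every combination of day and night findings. Section II does not say whether one criterion is enough or both are needed, so both readings are shown. *Meets* means that the participant is not sent to the device alone.

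| Room-air SpO₂ by day | Night criterion | Section VI (no arm named) | Section II, either suffices | Section II, both needed |
|---|---|---|---|---|
| below 88% | met | oxygen | meets | meets |
| below 88% | not met | oxygen | meets | device alone |
| 88% to just under 90% | met | oxygen | meets | device alone |
| 88% to just under 90% | not met | oxygen | device alone | device alone |
| 90% or above | met | not triggered | meets | device alone |
| 90% or above | not met | not triggered | device alone | device alone |

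1. Row 4 conflicts on either reading. The same participant is directed to oxygen by Section VI and, in the intervention arm, to the device alone by Section II.
2. Rows 2 and 3 conflict only if both criteria are needed.
3. Row 5 diverges the other way if one criterion suffices. Section II's wording then treats an intervention participant as having an oxygen indication, while Section VI's 90% rule does not reach an SOC participant with the same findings.
4. Row 4 tends towards more oxygen in SOC and row 5 towards more in the intervention arm, so the direction is not fixed.

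The 90% ceiling on oxygen titration during the diagnostic sleep study (Section VI) serves a different purpose and is not part of the conflict.

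**Illustration of scale, resting on assumptions.** The documents give no SpO₂ distribution, no oxygen effect and no allocation ratio.

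- From the documents: 60 completers and 80 enrolled (Section V; 60 / (1 − 0.25) = 80), and an expected 30-day readmission rate of 20.5% (Risks and Discomforts).
- Assumed: 1:1 allocation, giving 30 completers or 40 enrolled per arm; a share f of 5% to 30% in row 4; every such SOC participant given oxygen and no such intervention participant; a relative risk (RR) with oxygen of 0.5 to 1.0 in that group.
- Participants per arm in row 4 = n × f. For completers, 30 × 0.05 = 1.5 to 30 × 0.30 = 9. For enrolled, 40 × 0.05 = 2 to 40 × 0.30 = 12.
- Spurious 30-day difference = 0.205 × f × (1 − RR). At RR = 1.0 it is 0. At RR = 0.5 it is 0.205 × 0.05 × 0.5 = 0.005 to 0.205 × 0.30 × 0.5 = 0.031.

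The range is 0 to about 3.1 percentage points against the device, or at most about 40 × 0.031 = 1.2 readmissions per 40 participants. An RR above 1, or a preponderance of row 5 participants, would change the sign. The 20.5% is a readmission rate, not the rate of the composite primary endpoint, so this indicates scale and does not estimate the bias.

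**The case against.** The strongest reply is that Section VI already supplies one rule for everyone. It refers to participants without naming an arm, and it stands before the Randomization text, which says that assignment follows screening. The flow table also lists the room-air measurement ahead of randomisation. If every site works this way, oxygen is decided before allocation and no imbalance arises. This stands as far as it goes, and it is why the imbalance is possible and not certain. But the order of the text is not a timing rule, the flow table puts both steps in the same pre-discharge column, and Section II sets its own test at discharge.

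A second reply is that Section II forbids nothing. The reference to the device alone may describe only the night-time set-up for people without an oxygen indication, and the sentence before it provides for those going home on oxygen. That reading is available, so a reader who infers that Section II prohibits oxygen goes further than the text. It does not remove the conflict. A row 4 participant prescribed oxygen under Section VI would have it fed into the device under one sentence of Section II and would be on the device alone under the next.

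A third reply is that not everyone at 88–89% is affected, because night-time desaturation may qualify them under Section II as well. That is correct. If either criterion suffices, only those without it are in conflict.

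**Conclusion.** The plan is inconsistent as written. The two sections give different oxygen criteria, one of them is written for one arm only, and the guidelines that might settle the matter do not appear. A participant from 88% to just under 90% on room air without qualifying night-time desaturation meets conflicting directions if allocated to AVAPS-AE. Oxygen can therefore differ by arm after open-label allocation and bias the composite endpoint in either direction.

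A reader might infer that oxygen will differ by arm, or that the device effect cannot be separated from it. The documents do not support that. It depends on sites following Section II for the intervention arm and Section VI for SOC, and uniform use of Section VI would prevent it.

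The size cannot be determined from the documents. Under the assumed ranges it is modest, and both the share affected and the oxygen effect are assumptions. The conclusion rests on the wording, not on those figures.

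**What to change.** - The investigators should reconcile Sections II and VI into one oxygen rule. It should say whether one or both of the day and night criteria are needed, and the guidelines Section VI refers to should be supplied or the reference deleted. Which threshold applies is a clinical decision, and none is proposed here.
- State that the rule applies identically in both arms and that its result is determined and recorded before randomisation.
- Record oxygen at baseline and at discharge, with any later change, and report it by arm.
- If an adjusted analysis is wanted, prespecify it on pre-randomisation room-air SpO₂ or oxygen need. Do not adjust for oxygen use after randomisation, which allocation may itself have influenced.

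The cost is protocol wording and one or two case-report-form items. The room-air measurement is already scheduled before discharge, and the qualifying sleep study already records overnight saturation, although in participants who need oxygen at night that recording is made on oxygen.
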